Fourteen patients (7/arm) followed in the Children's Hospital Colorado Bariatric Surgery Center who meet inclusion criteria: 12-24yo; s/p SG or RYGB; and at 6-12 months post bariatric surgery^a, have either a) not achieved mean expected weight loss based on national standards and still have at least class 1 obesity or b) remain severely obese (\geq 120% of 95%ile or BMI \geq 35kg/m2 for 12-17yo; BMI \geq 35kg/m2 for 18-24yo) will be randomized 1:1 to pharmacotherapy + SOC^b or placebo + SOC in double-blind fashion. Expected weight loss at 6, 9, and 12 months postoperatively will be defined as a \geq 26%, \geq 28%, and \geq 31% decrease in weight, respectively, from preoperative weight (within 1 week of surgery) as was observed in the Teen-LABS study.⁷

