Exclusion criteria: absolute contraindication to phentermine or topiramate (i.e. phentermine: history of coronary artery disease, stroke, arrhythmia, congestive heart failure, uncontrolled hypertension), hypersensitivity to sympathomimetic amines, current or recent (within 14 days) use of monoamine oxidase inhibitors, glaucoma, or hyperthyroidism; topiramate: hypersensitivity to topiramate, history of nephrolithiasis), concomitant use of phenytoin, carbamazepine, or carbonic anhydrase inhibitors (e.g. zonisamide, acetazolamide, or dichlorphenamide), use of anti-obesity medication within 6 months of screening, initiation of a new medication associated with weight loss or gain within 30 days of screening, hypothalamic obesity, unmanaged (e.g. without medications and/or psychotherapy) clinically significant (determined by a mental health professional using diagnostic instruments and/or clinical interview) depression or anxiety, history of any suicidal behavior within 30 days of screening or any suicidal ideation with either some intent to act or with intent and a specific plan within 30 days of screening, history of severe psychiatric disorders (i.e. schizophrenia), severe hepatic impairment (ALT >10x upper limit of normal or known synthetic liver dysfunction), moderate or severe renal impairment (GFR <30mL/min/1.73m²), inability to meet minimum nutrition requirements, current pregnancy/plans to become pregnant for 16 weeks from study drug start date, and any females without a long acting reversible contraceptive (LARC) who do not commit to using 2 forms of birth control. (Of note, the vast majority of female patients undergoing surgery have a LARC placed intra-operatively, significantly reducing pregnancy risk during the trial). Patients on medications for hypertension, dyslipidemia, depression, and anxiety should be on these at a stable dose for >4 weeks prior to study enrollment, and on contraception for >7 days prior to study enrollment.

- Maximum number of subjects (patients + parent/guardian/LAR counted separately) needed to consent at all sites: 60
- Maximum number of local subjects (patients + parent/guardian/LAR counted separately) that will be consented, including screen failures and withdrawals: 60
- Number of local subjects (patients + parent/guardian/LAR counted separately) necessary to collect sufficient data to answer the research question: 20

Recruitment and Informed Consent/Assent Plan:

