the participant in advance of the informed assent discussion using REDCap's survey distribution tool. The eAssent form is designed to allow the participant to navigate forward and backward through the entire form and to access the form at a later time if desired. During the informed assent discussion, the potential participant's questions will be answered and at the end, the participant will verbally confirm they agree to be in the study. Because there can only be one signature ("certifier") for each REDCap eAssent form, there are separate REDCap eAonsent forms for the adolescent/young adult and the researcher presenting the form. The eAssent gives subjects the option to download a copy of the signed form. If a participant refuses or is unable to eAssent but is still interested in participating, a physical assent will be collected by the study team at the next inperson visit to the bariatric surgery center.

C. Study Design and Research Methods

Figure 1. Study Design

The pharmacotherapy group will receive oral phentermine and immediate release topiramate in combination, up-titrated to goal doses of 16mg and 100mg, respectively over 4 weeks*, then maintained at this dose for 8 additional weeks. Topiramate is gradually down-titrated during weeks 13 and 14 to prevent possible discontinuation symptoms.

Dosing Schedule^{†,§}

Uptitration:

- Week 1: 4mg phentermine + 25mg immediate release topiramate
- Week 2: 8mg phentermine + 50mg immediate release topiramate
- Week 3: 12mg phentermine + 75mg immediate release topiramate

Goal Dose:

- Weeks 4-12: 16mg phentermine + 100mg immediate release topiramate **Discontinuation (at study Visit 4)**:
- Week 13: Discontinue Phentermine + Decrease topiramate to 50mg
- Week 14: Decrease topiramate to 25mg for 7 days, then discontinue
- (*) Participants who do not tolerate goal doses will be maintained at the highest tolerated dose. (§) Per existing literature³⁴ and discussion with pharmacy, participants with moderate hepatic impairment (ALT >3x ULN but <10x ULN on two consecutive measures outside of acute illness, and no evidence of hepatic synthetic dysfunction), will follow the same dosing schedule, with doses reduced as needed

based on side effects (See Procedure for Study Drug Dose Reduction/Discontinuation).

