Nausea, Vomiting, Diarrhea	DSMP				
Rare, but Serious ⁴⁰					

Acute myopia, Secondary angle closure glaucoma	DSMP
Oligohidrosis, Hyperthermia	DSMP (including temperature at every study visit)
Metabolic acidosis	Bicarbonate at enrollment, visit 2, and visit 4
Suicidal ideation/attempt	DSMP with assessment at every study visit
Fetal toxicity	Pregnancy tests at enrollment and every study visit
(Pregnancy Risk Factor Category D- positive evidence of risk)	Requirement for females to either have a LARC (majority) or documented commitment to use 2 forms of birth control
Withdrawal symptoms	Gradual discontinuation at the end of the study
Hyperammonemia and encephalopathy	Drug interaction check; DSMP
Kidney stones	BMP at enrollment, visit 2, and visit 4; Drug interaction check; DSMP
Topiramate-Ethanol interaction (potential to cause increased CNS depression)	Counseling about alcohol avoidance, and specific language about this risk in the consent/assent

Methods for systematically assessing changes in mood, suicidality, and cognition.

Mood:

Changes in mood will be systematically screened for using the Center for Epidemiologic Studies Depression Scale (CES-D). This is a 20-item self-report questionnaire that covers areas including depressed mood, feelings of guilt/worthlessness, helplessness, psychomotor retardation, loss of appetite and sleep disturbance over the previous week. ⁴⁶ This instrument has yielded adequate internal reliability that is robust to age, clinical vs. nonclinical setting, and risk of bias. ⁴⁷ The original version of the measure is appropriate for individuals 12 years of age and older. The CES-D is routinely administered to individuals receiving care at the Children's Colorado Bariatric Surgery Center at every follow-up pre-operative and post-operative clinic appointment.

The proposed study will additionally administer the CES-D at all study visits not aligned with a clinical visit and will be scored by the PI or professional research assistant. A CES-D score <20 indicates no to mild depressive symptoms. And a CES-D score ≥20 indicates elevated depressive symptoms. This is based on a metaregression that supported higher cut points having better diagnostic accuracy.⁴⁷

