- **5. Will any formal interim analysis be performed?:** Interim assessments of feasibility, acceptability, and safety per above will be performed, but there will be no formal interim analysis for this 12-month study.
- **6. Are there defined** participant **discontinuation criteria?**: There are no *participant* discontinuation criteria. However, there are defined *drug* discontinuation criteria as follows:
 - a) Development of an anaphylactic allergic reaction, pulmonary hypertension, evidence of new valvular heart disease, uncontrolled systemic hypertension, new arrhythmia (including persistent tachycardia), severe anxiety unresponsive to dose decrease, psychiatric disorder that cannot be adequately treated with psycho- and/or pharmacotherapy at the discretion of the study's clinical psychologist, serotonin syndrome, or pregnancy during the pharmacotherapy intervention will lead to discontinuation of phentermine.
 - b) Development of an anaphylactic allergic reaction, nephrolithiasis, severe, persistent cognitive difficulties, psychiatric disorder that cannot be adequately treated with psychoand/or pharmacotherapy at the discretion of the study's clinical psychologist, new acute myopia or secondary angle closure glaucoma, severe metabolic acidosis, hyperammonemia with encephalopathy, or pregnancy during the pharmacotherapy intervention will lead to discontinuation of topiramate.
 - c) If one medication is stopped secondary to the criteria above, the participant, if in agreement, will be continued on the other medication as monotherapy.
 - d) With consent, participants for whom one or both medications are stopped will continue to be followed according to the proposed study timeline.

7. How will the PI/research team determine if an adverse event (AE) is related to either of the study drugs?

Relatedness will be defined according to the National Institutes of Health National Institute on Aging Data Safety and Monitoring Plan Toolkit template (https://www.nia.nih.gov/research/dgcg/clinical-research-study-investigators-toolbox/data-and-safety-monitoring) as follows:

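### The drug-stopping rules leave a participant with new angle closure glaucoma on phentermine by default, although the protocol lists glaucoma as a contraindication to phentermine

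*Combined protocol and SAP*

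**What the plan says.** Question 6 of the Data and Safety Monitoring Plan (Section IV.D) sets no criteria for withdrawing participants, but it does set criteria for stopping each drug.

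- Rule (a) lists the events that stop phentermine. None concerns the eye. The list ends: "serotonin syndrome, or pregnancy during the pharmacotherapy intervention will lead to discontinuation of phentermine".
- Rule (b) lists the events that stop topiramate, among them "new acute myopia or secondary angle closure glaucoma, severe metabolic acidosis". It ends: "hyperammonemia with encephalopathy, or pregnancy during the pharmacotherapy intervention will lead to discontinuation of topiramate".
- Rule (c) covers what follows when only one drug is stopped: "If one medication is stopped secondary to the criteria above, the participant, if in agreement, will be continued on the other medication as monotherapy".

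The exclusion criteria in Section IV.B give the absolute contraindications, phentermine first and topiramate second. The text where one list passes to the other reads: "use of monoamine oxidase inhibitors, glaucoma, or hyperthyroidism; topiramate: hypersensitivity to topiramate".

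Table 2 has a row for "Acute myopia, Secondary angle closure glaucoma" among the rare but serious topiramate reactions. The mitigation it gives is the Data and Safety Monitoring Plan itself.

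A footnote to the dosing schedule in Section IV.C also points to another text: "See Procedure for Study Drug Dose Reduction/Discontinuation". No section with that title is in the document reviewed.

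**The concern.** Rule (c) makes continuation on the other drug the default and exempts no trigger. Its only condition is that the participant agrees, and agreement is not a check for contraindications. If the event that stops topiramate is itself a contraindication to phentermine, the rule points the wrong way.

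At stake is the safety of a participant, possibly as young as 12, with an eye condition that the protocol classes as serious. A study physician who wanted to stop phentermine as well would have to depart from rule (c) to do it.

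**Working it through.** No figure in the plan needs reproducing. The check sets the two stopping lists against the contraindication list and then sizes the exposure.

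**Step 1: sort the events in rules (a) and (b).** Each rule names 9.

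| Stops | Events | Count |
|---|---|---|
| Both drugs | anaphylaxis; psychiatric disorder not adequately treatable; pregnancy | 3 |
| Phentermine only | pulmonary hypertension; new valvular disease; uncontrolled hypertension; new arrhythmia; severe anxiety despite a lower dose; serotonin syndrome | 6 |
| Topiramate only | nephrolithiasis; severe persistent cognitive difficulty; acute myopia; secondary angle closure glaucoma; severe metabolic acidosis; hyperammonemia with encephalopathy | 6 |

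Distinct events: 9 + 9 − 3 = 15. Rule (c) acts only where one drug is stopped: 15 − 3 = 12.

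**Step 2: compare each one-drug event with the Section IV.B contraindications to the drug that continues.**

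- Topiramate stopped, phentermine continues. The phentermine list is coronary artery disease, stroke, arrhythmia, heart failure, uncontrolled hypertension, hypersensitivity to sympathomimetic amines, current or recent monoamine oxidase inhibitor use, glaucoma and hyperthyroidism. Matches: 1 of 6 (glaucoma).
- Phentermine stopped, topiramate continues. The topiramate list is hypersensitivity and past nephrolithiasis, followed by the interacting drugs. Matches: 0 of 6.

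Conflicts under rule (c): 1 of 12.

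**Step 3: ask whether stopping both drugs is implied.** The drafting suggests not. The three events that stop both drugs are written out in both rules, as the two closing phrases on pregnancy show. Glaucoma appears in one rule only, so rule (c) applies to it.

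**Step 4: look for an exception elsewhere in the text.** The Table 2 row leads back to the same rules. The study-level stopping rule (question 8) covers only drug-related deaths and life-threatening drug experiences. The Safety Officer approves stopping criteria, but no glaucoma exception is recorded.

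**Step 5: size the exposure.** Section IV.B gives the number per arm: "Fourteen patients (7/arm) followed in the Children's Hospital Colorado Bariatric Surgery Center". About 7 people therefore take active drug; in the placebo arm the continued tablet would be placebo. The documents give no event rate, so the risk per participant, p, is assumed. The chance of at least one case is 1 − (1 − p)^n.

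| Assumed p | n = 7 |
|---|---|
| 0.01% | 1 − 0.9999^7 = 0.07% |
| 0.1% | 1 − 0.999^7 = 0.7% |
| 1% | 1 − 0.99^7 = 6.8% |

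At the minimum of 5 per arm in Section IV.F, the two ends become 1 − 0.9999^5 = 0.05% and 1 − 0.99^5 = 4.9%.

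**The case against.** The best argument against the point is that the separate dose reduction and discontinuation procedure may already deal with it. Question 6 gives no dose-reduction steps, so part of the operating rules evidently sits elsewhere, and a study physician would hold that text. This stands as a limit: the finding is about the text reviewed. Even if the procedure does make an exception, rule (c) would contradict it and need aligning.

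A second argument is that Section IV.B governs entry, not treatment, and that rule (a) was never meant to restate every phentermine contraindication; stroke and hyperthyroidism, for instance, are missing from it too. Both observations are correct. But several entry contraindications do carry over: arrhythmia and uncontrolled hypertension into rule (a), nephrolithiasis into rule (b). Glaucoma also differs from the missing items, because question 6 names it as an on-study event and then directs what happens to the other drug.

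Third, the stopping lists can be read as a minimum, with clinical judgement on top. Study physicians examine participants at every visit, and the investigator and the clinic's medical director manage physical side effects. These safeguards make harm less likely, and a careful clinician would probably stop phentermine. They do not change what rule (c) directs.

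Fourth, a bracket in the exclusion list closes before glaucoma is reached. The topiramate label that follows still makes the phentermine reading the natural one, and on any reading glaucoma bars entry.

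Finally, the probability range rests wholly on assumed risks, and it is the chance of the event, not of harm. Harm also requires that the participant agrees and that phentermine is in fact continued. That is fair: the range shows scale only, and the count of 1 in 12 describes list entries, not risk.

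**Conclusion.** The concern holds on the text reviewed. Rules (b) and (c) together make phentermine alone the default after new secondary angle closure glaucoma, against the protocol's own contraindication list. It is a single, specific omission: 1 of the 12 events on which rule (c) acts.

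The conclusion assumes that glaucoma belongs to the phentermine part of the exclusion list and that the cited procedure contains no exception. The probability is low (0.07% to 6.8% for at least one case among 7, on assumed risks), and the trial's estimates, sample size and feasibility endpoints are untouched. The rule should still be corrected, because the event is serious and following the rule as written gives an unsafe result.

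**What to change.** Either add new glaucoma to rule (a), or limit rule (c) to cases where the event that stopped the first drug is not a listed contraindication to the remaining one. The second option also covers any later addition to the lists. Check the separate dose reduction and discontinuation procedure and give it matching wording.

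The cost is one clause and the usual amendment steps: approval by the Safety Officer, whose remit includes these criteria, then the IRB and the IND file, since the IND covers use as this protocol defines it. No visits, tests or participants are added. The one drawback is that a participant with this event would lose both drugs instead of one. Follow-up could continue with consent, as rule (d) already provides.
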